For the base case analysis, we will use the trial duration as time horizon and in addition an extended lifetime horizon. The modeled future costs and quality-adjusted life years (QALYs) will be discounted at the annual rate of 3% and averaged for the two scenarios. To take into account patient heterogeneity and parameter uncertainty, the decision model's equations for event rates, quality of life, and costs will be regenerated in bootstrap datasets, each with the same size of 2354 patients. Using the decision models' output of each bootstrap (probabilistic cost-effectiveness analysis), we will construct incremental cost effectiveness (ICE) scatterplots. Second, we will calculate average net health benefits for HCR and PCI. The net health benefit is defined as the difference between the health effect in QALY associated with the chosen intervention and the minimum health effect that society would demand in return for the investment: QALY – QALY/cost-effectiveness threshold.³⁵ Recently recommended cost-effectiveness thresholds of \$50,000, \$100,000, and \$200,000 per QALY will be considered.³⁶ In addition, 95% confidence intervals will be calculated for the difference in mean QALYs, costs and net health benefits by comparing the two scenarios across bootstraps. Deterministic sensitivity analyses will be performed to explore the robustness of the findings, including variations in discount rates, different time horizons, and changes in costs, survival and QoL due to increased use and experience.

Missing Data

For participants who are lost to follow-up we will use all the information available up to the time of loss to follow-up. If the data are missing at random (MAR), that is, the probability of being missing depends only on observed values, then likelihood-based methods such as mixed-effects models will be used for analysis without bias.³⁷ If the fraction of missing data is small we expect that even non-ignorability will have a negligible effect on the final estimates. If the extent of missingness is large compared to the effect size, we will use the multiple imputation procedure proposed by Rubin and Little.^{38, 39}

Safety Analysis

The DSMB will receive regular reports on MACCE and the individual components of MACCE, as well as other cardiovascular and bleeding events for all participants in the trial. As part of the

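### The net health benefit formula divides QALYs, not costs, by the threshold, so cost drops out of the statistic

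*Combined protocol and SAP*

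**What the plan says.** The passage is in the Analytical Plan, under Analysis of Secondary End-points, Cost-effectiveness. After describing the microsimulation and the bootstrap, the plan states: "Second, we will calculate average net health benefits for HCR and PCI". It gives the definition in words, "The net health benefit is defined as the difference between the health effect in QALY associated with the chosen intervention and the minimum health effect", and finishes the sentence with a formula: "minimum health effect that society would demand in return for the investment: QALY – QALY/cost-effectiveness threshold".

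The next sentence sets the thresholds at $50,000, $100,000 and $200,000 per QALY. The plan then commits to inference on the statistic: "95% confidence intervals will be calculated for the difference in mean QALYs, costs and net health benefits by comparing the two scenarios across bootstraps".

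Costs are available to the calculation. The same section says: "The modeled future costs and quality-adjusted life years (QALYs) will be discounted at the annual rate of 3% and averaged for the two scenarios". No other part of the document gives a different formula, and the Table of Changes does not mention this one.

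**The concern.** The verbal definition and the formula disagree. What society demands in return for an investment depends on the size of the investment, which is the cost. The formula puts QALYs where cost belongs, so the arm with more QALYs has the higher net health benefit whatever it costs, and the choice of threshold has almost no effect.

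This matters because comparative cost-effectiveness is named as a secondary outcome at the start of the Analytical Plan, and net health benefit is the only output that the section ties to the three thresholds. A programmer who implements the formula as printed would report a cost-effectiveness summary, with a confidence interval, that carries no cost information.

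**Working it through.** The plan reports no numerical net health benefit, so there is no figure to reproduce. The check uses units, algebra and an illustration.

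**Inputs from the plan.** The printed formula, the verbal definition, and the thresholds λ = $50,000, $100,000 and $200,000 per QALY. Write Q for mean QALYs, C for mean cost, and Δ for HCR minus PCI.

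**Units.**
- Printed second term: Q/λ = QALY ÷ ($/QALY) = QALY²/$. This cannot be subtracted from QALYs.
- Cost-based second term: C/λ = $ ÷ ($/QALY) = QALY. This can.

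**Algebra.**
- Printed: Q − Q/λ = Q × (1 − 1/λ). The multiplier is 0.99998 at $50,000, 0.99999 at $100,000 and 0.999995 at $200,000. The difference between arms is ΔQ times that multiplier, and C does not appear. In each bootstrap sample the net health benefit difference is the QALY difference times the same constant, so its 95% interval is the QALY interval shrunk by at most 1/50,000 = 0.002%.
- Cost-based: (Q − C/λ) differenced between arms is ΔQ − ΔC/λ. It is zero when ΔC = λ × ΔQ and negative above that.

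**Illustration.** The documents give no expected QALY or cost difference, so these values are assumed. Take ΔQ = 0.10 and let ΔC range from $0 to $50,000.

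| ΔC | λ = $50,000 | λ = $100,000 | λ = $200,000 |
|---|---|---|---|
| Printed formula, any ΔC | 0.099998 | 0.099999 | 0.0999995 |
| Cost-based, $0 | 0.100 | 0.100 | 0.100 |
| Cost-based, $5,000 | 0.000 | 0.050 | 0.075 |
| Cost-based, $10,000 | −0.100 | 0.000 | 0.050 |
| Cost-based, $15,000 | −0.200 | −0.050 | 0.025 |
| Cost-based, $50,000 | −0.900 | −0.400 | −0.150 |

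For example, at $15,000 and λ = $50,000: 0.10 − 15,000/50,000 = 0.10 − 0.30 = −0.20.

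With this ΔQ the sign changes at ΔC = 0.10 × 50,000 = $5,000, 0.10 × 100,000 = $10,000 and 0.10 × 200,000 = $20,000 for the three thresholds. A smaller gain gives way sooner. With ΔQ = 0.02 and ΔC = $5,000 the cost-based values are −0.080, −0.030 and −0.005, while the printed formula still gives about +0.020 at each threshold.

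**The case against.** The strongest reply is that this is a one-word slip that the sentence itself exposes. The definition before the colon is right, the thresholds are in dollars per QALY, and costs are modelled and discounted for both scenarios. An experienced health economist would probably see the intent and compute the right quantity. That is a fair reading, but it asks the analyst to depart from a prespecified formula without a documented correction. The citation does not settle the matter either. The superscript at that sentence is 35, and item 35 in the reference list is a paper on mixed-effects models in psychophysiology. A net health benefit methods paper is listed as item 37.

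The second reply is about reach, and it stands. The plan also says "we will construct incremental cost effectiveness (ICE) scatterplots", and it gives separate intervals for the differences in mean costs and mean QALYs. Those use cost properly, and a reader could work out the point estimate of net benefit from the two differences. The listed cost-effectiveness endpoints in the Endpoints section, costs and quality-adjusted life expectancy, do not depend on the formula.

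The third reply is that the reversal of sign is conditional. If the arms cost the same, the two formulas agree to within 0.000002 QALY in the illustration (0.10/50,000). That is also true. The size of the error in this trial depends on a cost difference that the documents do not give.

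**Conclusion.** The formula is wrong as written. It contradicts its own verbal definition, fails on units, and contains no cost. Followed literally, net health benefit and its bootstrap interval restate the QALY result to within 0.002% at all three thresholds.

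This conclusion rests only on the plan's definition and its dollar-per-QALY thresholds. How far the reported value would be off depends on assumed inputs: for a 0.10 QALY gain, nothing material at equal cost, about 0.30 QALY at $50,000 per QALY if HCR costs $15,000 more (0.10 against −0.20), and about 1.00 QALY if it costs $50,000 more (0.10 against −0.90).

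The defect is confined to one secondary health-economic statistic. The scatterplots, the cost and QALY intervals, the primary endpoint, the sample size and the type I error are untouched. It should be corrected before the economic analysis is programmed.

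**What to change.** Replace the second QALY in the formula with cost, so that for each arm net health benefit = QALYs − costs/cost-effectiveness threshold, computed in every bootstrap sample. State the incremental form as well: difference in QALYs − (difference in costs)/threshold, reported with its 95% interval separately at $50,000, $100,000 and $200,000 per QALY.

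The cost is a one-term edit plus one clarifying sentence in the analysis plan. The costs are already to be collected, modelled, discounted and bootstrapped, so no new data or procedures are needed.

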APPENDIX I: Canadian Cardiovascular Society Classification

Overview:

The Canadian Cardiovascular Society Classification of angina pectoris separates patients with anginal symptoms into groups based on the severity of their symptoms. The classification uses the extent of limitation on daily activities and the kind of physical activity which precipitates the anginal episode.

| Clinical Findings | Features | Grade |
|---|---|-------|
| No limitation of ordinary activity | Ordinary physical activity (such as walking or climbing stairs) does not cause angina. Angina may occur with strenuous rapid or prolonged exertion at work or recreation. | I |
| Slight limitation of ordinary activity | 
Angina may occur with
 
 • Walking or climbing stairs rapidly; • Walking uphill; • Walking or stair climbing after meals or in the cold in the wind or under emotional stress, or only during the few hours after awakening. • Walking more than 2 blocks on the level at a normal pace and in normal conditions • Climbing more than 1 flight of ordinary stairs at a normal pace and in normal conditions | II |
| Marked limitation of ordinary physical activity | 
Angina may occur after
 
 • Walking 1-2 blocks on the level or • Climbing 1 flight of stairs in normal conditions at a normal pace | III |
| Unable to carry on any physical activity without discomfort | Angina may be present at rest. | IV |

Campeau L. Grading of angina pectoris (Letter to the Editor). *Circulation*. 1976; 54: 522-523.

Appendix II: Quality of Life Measures

SHORT FORM – 12 (SF-12 version 2)

Your Health and Well-Being

This survey asks for your views about your health. This information will help keep track of how you feel and how well you are able to do your usual activities. Thank you for completing this survey!

For each of the following questions, please mark an in the one box that best describes your answer.

1. In general, would you say your health is:

| | | | | |
|----------------------------|----------------------------|----------------------------|----------------------------|----------------------------|
| Excellent | Very good | Good | Fair | Poor |
|  1 |  2 |  3 |  4 |  5 |

2. The following questions are about activities you might do during a typical day. Does your health now limit you in these activities? If so, how much?

| | | |
|--------------------------|--------------------------|--------------------------|
| Yes, limited a lot | Yes, limited a little | No, not limited at all |
|  |  |  |

a Moderate activities, such as moving a table, pushing a vacuum cleaner, bowling, or playing golf..... 1..... 2..... 3

b Climbing several flights of stairs 1..... 2..... 3

SF-12v2® Health Survey © 1994, 2002 Medical Outcomes Trust and QualityMetric Incorporated. All rights reserved.
 SF-12® is a registered trademark of Medical Outcomes Trust.
 (SF-12v2® Health Survey Standard, United States (English))

3. During the past 4 weeks, how much of the time have you had any of the following problems with your work or other regular daily activities as a result of your physical health?

| | All of the time | Most of the time | Some of the time | A little of the time | None of the time |
|---|---------------------------------|---------------------------------|---------------------------------|---------------------------------|----------------------------|
| a) Accomplished less than you would like |  1..... |  2..... |  3..... |  4..... |  5 |
| b) Were limited in the kind of work or other activities |  1..... |  2..... |  3..... |  4..... |  5 |

4. During the past 4 weeks, how much of the time have you had any of the following problems with your work or other regular daily activities as a result of any emotional problems (such as feeling depressed or anxious)?

| | All of the time | Most of the time | Some of the time | A little of the time | None of the time |
|--|---------------------------------|---------------------------------|---------------------------------|---------------------------------|----------------------------|
| a) Accomplished less than you would like |  1..... |  2..... |  3..... |  4..... |  5 |
| b) Did work or other activities less carefully than usual |  1..... |  2..... |  3..... |  4..... |  5 |

5. During the past 4 weeks, how much did pain interfere with your normal work (including both work outside the home and housework)?

| | Not at all | A little bit | Moderately | Quite a bit | Extremely |
|--|----------------------------|----------------------------|----------------------------|----------------------------|----------------------------|
| |  1 |  2 |  3 |  4 |  5 |

SF-12v2® Health Survey © 1994, 2002 Medical Outcomes Trust and QualityMetric Incorporated. All rights reserved.
 SF-12® is a registered trademark of Medical Outcomes Trust.
 (SF-12v2® Health Survey Standard, United States (English))

6. These questions are about how you feel and how things have been with you during the past 4 weeks. For each question, please give the one answer that comes closest to the way you have been feeling. How much of the time during the past 4 weeks...

| | All of the time | Most of the time | Some of the time | A little of the time | None of the time |
|--|-----------------|------------------|------------------|----------------------|------------------|
| | ▼ | ▼ | ▼ | ▼ | ▼ |

a. Have you felt calm and peaceful?..... 1..... 2..... 3..... 4..... 5

b. Did you have a lot of energy? 1..... 2..... 3..... 4..... 5

c. Have you felt downhearted and depressed?..... 1..... 2..... 3..... 4..... 5

7. During the past 4 weeks, how much of the time has your physical health or emotional problems interfered with your social activities (like visiting with friends, relatives, etc.)?

| | All of the time | Most of the time | Some of the time | A little of the time | None of the time |
|--|----------------------------|----------------------------|----------------------------|----------------------------|----------------------------|
| | ▼ | ▼ | ▼ | ▼ | ▼ |
| |  1 |  2 |  3 |  4 |  5 |

Thank you for completing these questions!

SF-12v2® Health Survey © 1994, 2002 Medical Outcomes Trust and QualityMetric Incorporated. All rights reserved.
SF-12® is a registered trademark of Medical Outcomes Trust.
(SF-12v2® Health Survey Standard, United States (English))

EURO QoL 5-D QUESTIONNAIRE

Check one box for each of the following six health dimensions.

Mobility

| | |
|---------------------------------------|----|
| I have no problems in walking about | 1. |
| I have some problems in walking about | 2. |
| I am confined to bed | 3. |

Self-Care

| | |
|---|----|
| I have no problems with self-care | 1. |
| I have some problems washing or dressing myself | 2. |
| I am unable to wash or dress myself | 3. |

Usual Activities (e.g. work, study, housework, family or leisure activities)

| | |
|--|----|
| I have no problems with performing my usual activities | 4. |
| I have some problems with performing my usual activities | 5. |
| I am unable to perform my usual activities | 6. |

Pain/Discomfort

| | |
|------------------------------------|----|
| I have no pain or discomfort | 7. |
| I have moderate pain or discomfort | 8. |
| I have extreme pain or discomfort | 9. |

Anxiety/Depression

| | |
|--------------------------------------|-----|
| I am not anxious or depressed | 10. |
| I am moderately anxious or depressed | 11. |
| I am extremely anxious or depressed | 12. |

Compared with my general level of health over the past 12 months, my health state today is:

| | |
|---------------|-----|
| Better | 13. |
| Much the same | 14. |
| Worse | 15. |

To help people say how good or bad a health state is we have drawn a scale (rather like a thermometer) on which the best state you can imagine is marked by 100 and the worst state you can imagine is marked by 0.

**Best
imaginable
health state**

We would like you to indicate on this scale how good or bad is your own health today, in your opinion. Please do this by drawing a line from the box below to whichever point on the scale indicates how good or bad your current health state is.

**Your own
health state
today**

**Worst
imaginable
health state**

Appendix III: New York Heart Association (NYHA) Classification

| Class | Patient Symptoms |
|------------------------|---|
| Class I (Asymptomatic) | No limitation of physical activity. Ordinary physical activity does not cause undue fatigue, palpitation, or dyspnea (shortness of breath). |
| Class II (Mild) | Slight limitation of physical activity. Comfortable at rest, but ordinary physical activity results in fatigue, palpitation, or dyspnea. |
| Class III (Moderate) | Marked limitation of physical activity. Comfortable at rest, but less than ordinary activity causes fatigue, palpitation, or dyspnea. |
| Class IV (Severe) | Unable to carry out any physical activity without discomfort. Symptoms of cardiac insufficiency at rest. If any physical activity is undertaken, discomfort is increased. |
